4 TREATMENTS

4.1 Study Treatment: Linagliptin

Definition of Investigational Product: A pharmaceutical form of an active substance or placebo being tested or used as a reference in a clinical study, including products already with a marketing authorization but used or assembled (formulated or packaged) in a way different from the authorized form, or used for an unauthorized indication, or when used to gain further information about the authorized form. In this protocol, the investigational product is Linagliptin.

Definition of Non-Investigational Product: Other medications used in the study as support or escape medication for preventative, diagnostic, or therapeutic reasons as components of a given standard of care. In this protocol, the non-investigational product is Insulin, Metformin, or both. Patients will continue on Insulin, Metformin, or both as per their study entry dose added to Linagliptin or placebo. As mentioned before, patients on oral hypoglycemic agents other than Metformin will not be invited to join the study as OHA plus DPP4 inhibitor could have a different effect on vasculature or hemopoetic CD34+ stem cells compared to insulin and DPP4 inhibitor.

This study is being conducted under FDA mandated guideline for use in type 2 diabetes. Though in this particular study Linagliptin is referred to as the investigational drug, it is not a novel drug and we should not need a separate IND for execution of this study.

4.2 Method of Assigning Subjects to a Treatment

Subjects, as per selection criteria below will be randomized to treatments using a permuted block design, developed by the Epidemiology & Biostatistics Research Core. This approach ensures groups will be approximately balanced at any time during the study and at study completion.

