Our study population will include equal numbers of adult male and female Type 2 diabetes (T2DM) patients aged 40-70 years, enrolled in both arms of the study. Patients will be treated with 5 mg of Linagliptin or placebo for 12 weeks and with adequate lifestyle modification for 16 weeks (as per American Diabetes Association guidelines). This time interval has been previously shown to be adequate to observe changes to Endothelial Progenitor Cells (EPCs), (5, 6).

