As per recent clinical guidelines (2), all patients at entry will receive dietary advice by study coordinator, diabetes educator, or registered dietician specifically geared towards type 2 diabetes patients. They will be advised to adhere to 150 minutes of weekly aerobic exercise (50-70% of maximal heart rate). Patient's activity will be monitored using accelerometers and will be downloaded at visit 2 and visit 3 by the study staff.

Subjects will be taking 5.0 mg of Linagliptin or placebo. Dose titration of insulin will be allowed so that the HbA1C is maintained below 10%.

Visits with outcome measurements will be scheduled for the morning while overnight fasting (except water) to reduce diurnal variability, and clinical parameters will be obtained at scheduled office visits as depicted in the study schema and will be measured at each outcome visit as follows:

Week -4: Subjects will be screened and eligibility will be verified based on physical and laboratory tests. Equal numbers of male and female patients will be recruited. All patients will be educated on the recommended lifestyle changes of maintaining a level of aerobic activity of 150 minutes/ week (non-supervised) and adherence to a healthy diet as advised by the study coordinator, a diabetes educator, or a dietitian as part of the type 2 diabetes patient management plan [2]. We will allow 4 weeks for the patients to reach a steady state while implementing diet and exercise changes.

Week 0: At this stage patients will be randomized into the study. Subjects will have the first set of measurements. We will make sure that patients still meet the inclusion criteria. They will be started on medication or placebo and will be encouraged to continue 150 minutes/week of moderate physical exercise and dietary management for the remainder of the study.

Weeks 0, 6 and 12: Subjects will all have the same measurements and will continue on study medication or placebo. All primary and secondary measures as outlined before will be carried out.

The cellular outcome measures are as follows:

From MNC population (pre magnetic column sorting):

A. FACS Analysis, 1 million cells in each tube/assay column. 12 tubes-- total 12 million. (All labelling antibodies are obtained from Miltenyi Biotec except Sytox blue-Invitrogen and anti-VEGFR2/KDR-R&D systems)

1. Unlabelled

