5 STATISTICAL CONSIDERATIONS

Statistical Analysis:

Sample Size Estimation:

The total sample size requested, accounting for attrition over the 12-week period, is 20 subjects per group or 40 subjects total. We plan to allow for 25% attrition (drop out), therefore plan to screen 55 patients over three years.

Sample size estimates were based on the effects of exercise on CD34+/KDR+ cells and VEGF, as described in the literature (47-50).

This is a pilot study and accurate power calculation is not feasible.

The effect of a single session, as well as extended training, on healthy subjects or those with existing cardiovascular conditions appears to increase the CD34+/KDR+ cells and VEGF.

To compute sample size we used the approach suggested by Diggle, Liang, & Zeger (1994)(51) which compares the rates of change in the two study groups over time. This approach incorporates the number and interval of time points and the correlation among repeated measures. For this study, we will employ one baseline and two follow-up measures at 6 and 12 weeks. Further, we will assume a correlation 0.60 among repeated measures of the outcome. We consider this a conservative estimate since Frison and Pocock (1992) (52) suggest a correlation of 0.65 as reasonable in the absence of an existing estimate. We also note that as this correlation increases, statistical power also increases.

The results in the table below show the expected mean difference in study groups at the end of follow-up, as well as the average rate of change in the two groups at 80% power and 90% power. To estimate the effect of Linagliptin on the CD34+/KDR+ cells, we expect that the effect would be at least 25% greater than the effect seen for exercise alone. Using the results from Sandri et al. (2005)⁴⁹ for the rate of change and the variability, the CD34+/KDR+ cells increased an average rate of about 4/wk with a standard deviation of about 15. Thus, for a 25% increase in the rate of change for the CD34+/KDR+ cells due to Linagliptin, a sample size of 18 subjects per group would provide about 84% power, assuming measures taken at baseline and 2 equally-spaced time points over 12 weeks. At the conclusion of follow-up, we would expect study groups to differ by an average of 12 cells. If the effect of Linagliptin is only 20%, a sample of 18 would provide about 70% power, whereas a sample of 20 would provide about 73% power.

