To estimate the effect of linagliptin on CD34+/KDR+ cells, we originally proposed a sample size of 20 per group in 2 groups, giving us power = .73, assuming alpha=.05, between time points of .60 and equal allocation between groups. Thus, the group x time interaction effect size we were modeling was an interaction that explained 3% of total variance, or a partial eta-square = .0291. Using 3 groups (Insulin only, metformin only, metformin + insulin), with the same effect size, we would achieve this same level of power using a total sample size of 51 (17 per group). However, given the relatively small numbers of potential participants with insulin-only (n=21) and insulin+metformin (n=54), and the relative large number with Metformin only (260), we will need to change the allocation ratio between groups. Maintaining the same total sample size as originally proposed (40), we will allocate patients from each group in the following numbers: **Metformin only (22), Metformin+insulin (12), Insulin only (6)**. We recognize that we will be underpowered for comparisons between the Metformin + insulin versus Insulin groups. However, comparisons with the Metformin-only group will still have reasonable power. Given the small number of potential patients with Insulin-only, this is a feasible strategy for including this group in the analysis.

Data Analysis.

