The distributional assumptions of all measures will be examined. Means and standard deviations will be computed for continuous measures and proportions for categorical variables. Graphical representations of the mean group slopes and individual slopes will be generated and inspected. Study groups will be compared to determine whether any imbalance between the groups on patient characteristics remain after randomization. If imbalance is evident, by inspection, all models will be adjusted for the unbalanced covariates. Change in outcome over time will be examined using a multilevel approach with linear mixed models (LMM) (53, 54). The longitudinal multilevel modeling approach will enable us to examine characteristics of within-person change, as well as between-group differences that may influence change. LMMs handle missing data more efficiently than traditional ANOVA designs. In the linear mixed models, the patient is considered a random effect and the outcome measured at specific time points is nested within patient. In an initial model containing only the variable TIME, we will use a likelihood ratio test to determine whether a random effect for time should be modeled.

The model below represents a random intercept for patient and a random coefficient for TIME.

$$Y_{ij} = \beta_0 + \beta_1 Time_{ij} + u_{i0} + u_{i1} Time_{ij} + \varepsilon_{ij}$$

We will examine whether TIME may be modeled linearly by testing the added contribution of TIME (represented with two indicator variables) to a model with TIME as a single continuous variable. Assuming time may be modeled as a continuous variable, subsequent analyses will add study group and other patient characteristics as covariates. We are particularly interested in whether there is a significant interaction between study group and time, adjusting for other patient level covariates. A significant interaction would indicate that the slopes in outcome over time differ by study group. If the global test of interaction is significant, subsequent significance testing of the pairwise comparisons of group slopes group will be adjusted for multiple comparisons. The model also includes coefficients for the group-by-time interactions and random effects for patient and time.

$$Y_{ij} = \beta_0 + \beta_1 Time_{ij} + \beta_2 Group_i + \beta_3 (Time_{ij} \times Group_i) + u_{i0} + u_{i1} Time_{ij} + \varepsilon_{ij}$$

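### Section 4.2 names no stratification factor, so nothing delivers the stated sex balance in both arms or balances the arms within the 22/12/6 background-therapy groups, and the adjustment set is left to be chosen after the data are seen

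*Combined protocol and SAP*

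**What the plan says.** Section 4.2 gives the allocation method in one sentence: patients are "randomized to treatments using a permuted block design". It adds: "This approach ensures groups will be approximately balanced at any time during the study and at study completion". No block size, number of lists or stratification factor is given there or elsewhere in the document.

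Two other places set expectations about composition:

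- **Sex.** Section 3.1 describes "equal numbers of adult male and female Type 2 diabetes (T2DM) patients aged 40-70 years, enrolled in both arms of the study". The methods text under section 4.5 puts it as a recruitment target: "Equal numbers of male and female patients will be recruited".
- **Background therapy.** Section 5 (Sub-Group Subject Number Breakdown) sets the numbers at "Metformin only (22), Metformin+insulin (12), Insulin only (6"), which sum to 40. These are totals for the whole trial, not per arm. The same paragraph discusses power for comparisons between the therapy groups.

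On residual imbalance, section 5 (Data Analysis) says: "If imbalance is evident, by inspection, all models will be adjusted for the unbalanced covariates". It also says that later models will include further patient characteristics and that the group-by-time interaction will be tested with patient-level covariates in the model. Neither sex nor background therapy is named.

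**The concern.** Permuted blocks without strata control one thing, the number of patients per arm. They do not control how men and women, or the three therapy groups, divide between linagliptin and placebo. The section 3.1 statement on sex therefore has no mechanism behind it, and the therapy groups that section 5 intends to analyse may divide unevenly between the arms. With 20 per arm, chance splits can be large.

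The analysis safeguard is loose. A covariate enters if someone judges it unbalanced on inspection, with no threshold and no list, and the other covariates are unnamed. With several cellular, gene-expression and renal primary measures, this makes the model for each outcome depend on a choice made after the data are seen.

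**Working it through.** **Plan's own figure.** The document gives no probability of imbalance to reproduce. Its variance inputs matter in step 4, so I checked those. With SD 15, correlation 0.60 and weeks 0, 6 and 12 (sum of squares about the mean 36 + 0 + 36 = 72), the slope SD is 15 × √(0.40/72) = 1.118 cells per week. For a 20% effect (0.8 per week) and 20 per group, this gives power 0.732 at one-sided 0.05, against the stated 73%. (Two-sided 0.05 gives 0.619; sidedness is not stated, which is a separate matter.)

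**Step 1: chance splits, exact.** Inputs: 40 patients, 20 per arm (section 5); 20 men and 20 women (sections 3.1 and 4.5); therapy groups 22/12/6 (section 5), so any insulin = 12 + 6 = 18. If K patients have a characteristic, the number k in one arm follows

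P(k) = C(K,k) × C(40−K, 20−k) / C(40,20).

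For sex, P(10) = C(20,10)² / C(40,20) = 0.248.

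| Factor | K | Exactly even | Differ by 4 or more | Differ by 6 or more |
|---|---|---|---|---|
| Men | 20 | 25% | 34% (12:8 or worse) | 11% |
| Any insulin | 18 | 25% | 34% (11:7 or worse) | 11% (12:6 or worse) |
| Metformin + insulin | 12 | 27% | 30% (8:4 or worse) | 8% |
| Insulin only | 6 | 34% | 18% (5:1 or worse) | 2% (6:0) |

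Metformin only (22) is the complement of any insulin and has the same figures. Simulated unstratified blocks of 4 and of 40 (assumed, as block size is not given) agree with these.

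**Step 2: both factors together.** Take sex as independent of therapy (assumed) and call a difference of 4 or more patients visible.

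- Sex and any insulin: both 0.343 × 0.341 = 0.117, about 12%; at least one 0.343 + 0.341 − 0.117 = 0.567, about 57%.
- Sex and all three therapy groups, by simulation: at least one therapy group 50–51%; sex or a therapy group 67–68%; both factors 17%.

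**Step 3: what an imbalance does to the planned test.** The test in section 5 is the group-by-time coefficient. With complete data at three equally spaced visits, its estimate is the arm difference in mean (week 12 − week 0)/12. A constant difference in level between insulin users and others cancels. In a simulation of the plan's model with a 12:6 split, a 7.5-cell level difference and a true effect of 12 cells, the mean estimate was 12.3 (simulation SE 0.29), so no clear shift. Adding the factor as a main effect alone changed the estimate by less than 1e-12. Only a difference in change over time matters, and only a factor-by-time term removes it.

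**Step 4: size if there is such a difference.** Assume that insulin users' 12-week change differs by 0.5 SD = 7.5 cells; the documents give no figure. Then:

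- 11:7 split: (11/20 − 7/20) × 7.5 = 1.5 cells.
- 12:6 split: (12/20 − 6/20) × 7.5 = 2.25 cells, or 2.25/12 = 19% of the 12-cell planned difference.

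The standard error of the 12-week contrast is 12 × 1.118 × √(2/20) = 4.2 cells, so 2.25 cells is about half a standard error.

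**The case against.** The strongest case against runs as follows. Chance imbalance under randomisation is not bias in expectation and is already covered by the test's type I error. Section 4.2 is silent on strata; it does not exclude them. The 22/12/6 figures are trial-wide, only section 3.1 mentions sex by arm, and it need not mean exactly 10/10. Section 5 already plans covariate adjustment beyond the inspection rule. This is a 40-patient pilot, and how many patients remain to be randomised is unknown.

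Most of this stands and limits the point. It does not remove two things: a stated composition by arm with no mechanism to deliver it, and an adjustment set that is not fixed in advance.

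Three stronger readings are tempting, and the documents do not support them:

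- *Both factors will probably be unbalanced.* This is true only if unbalanced means anything short of exactly equal (68%). For differences of 4 or more, both occur together in 12% to 17%.
- *The plan itself says that metformin or insulin background alters the drug's effect on CD34+ cells.* Section 4.1 says this of oral agents other than metformin, as the reason for excluding them. The comparisons between therapy groups planned in section 5 show that the authors care about the factor, but not that it modifies the effect.
- *A 12:6 split biases the result by 19%.* This needs a split seen in 11% of trials and an assumed difference in change. A difference in level would not do it.

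**Conclusion.** The point holds in a limited form. As written, the plan does not deliver the sex balance stated in section 3.1 (25% chance of exactly 10/10, 34% of 12:8 or worse), and it does not balance the arms within the therapy groups (any insulin 11:7 or worse 34%; insulin only 5:1 or worse 18%). A visible imbalance in at least one factor is more likely than not.

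The effect on the primary comparison is conditional: none on the group-by-time estimate if the factor relates only to level, and about 2.3 cells for a 12:6 split if 12-week changes differ by the assumed 7.5 cells. The figures rest on 20 per arm, 20 men and 20 women, filled therapy quotas, sex independent of therapy, and no unstated strata. This is a cheap improvement to the plan and does not undermine the trial.

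**What to change.** 1. **Allocation.** State whether the lists are stratified. If they are not, then for patients still to be randomised, stratify the permuted blocks by sex and background therapy (metformin only versus any insulin) with small blocks, and record the block size in a restricted document. Reword section 3.1 if balance by sex within arm is not meant as a design property.
2. **Analysis.** Before unblinding, replace the inspection rule with pre-specified terms for sex and background therapy, each with its interaction with time, in the mixed model for every outcome. Name any other covariates at the same point.

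**Cost.** A new pharmacy list and a short change to section 5. With four strata used from the first patient, the 34% risks fall to about 0–2% (blocks of 2 or 4), but incomplete blocks give a 6–9% chance that arm totals differ by 4 or more. With linear time the model gains four parameters (two main effects, two interactions). The insulin-only split within the any-insulin stratum stays uncontrolled.

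The gain from stratifying shrinks as fewer patients remain. Version 6.9 is dated June 2017, and the synopsis gives September 2015 to September 2018 for entry. If none remain, the analysis change can still be made before data lock and unblinding under section 4.4.

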4.3 Selection and Timing of Dose for Each Subject

The recommended dose of Linagliptin is 5 mg PO will be given once daily. Linagliptin can be taken with or without food.

4.3.1 Dose Modifications

No dose modification is necessary in CKD stage 1-3

4.4 Blinding/ Unblinding

Blinding is critical to the integrity of this clinical study. However, in the event of a medical emergency or pregnancy in a subject, **in which knowledge of the investigational product is critical to the subject's management**, the blind **for that subject** may be broken.

Before breaking the blind of an individual subject's treatment, the investigator should have determined that the information is necessary, i.e., that it will alter the subject's immediate management. In many cases, particularly when the emergency is not investigational product-related, the problem may be properly managed by assuming that the subject is receiving active product without the need for un-blinding.

End of Study Unblinding Protocol

Upon completion of the research study, we will undergo the following protocol in order to unblind the research data.

Unblinding is the process by which the allocation code is broken so that the investigator, clinical staff and the trial statistician becomes aware of which intervention each subject enrolled in the research study was taking.

Unblinding at the end of the study is required in order to make unmasked analysis in accordance with the study analysis plan. It is also conducted in order to inform the participants of which investigational product they were assigned to.

Time to unblind:

Unblinding shall be conducted when all subjects enrolled in the research study have finished treatment, and all follow up visits. There must be no plan to recruit any more subjects in the research study. Additionally, all data points and outcome measures for each research subject must have been collected, and ideally compiled. Prior to unblinding there will be a data lock on clinical outcome measures and basic side outcome measures and associated research data collected for the study.

Procedure to unblind

Once data (from both the clinical and the basic science side) and has been compiled and is data locked, the investigator can choose to unblind. The Principal Investigator must contact the study sponsor, and receive permission to un-blind. If, for unforeseen reasons, at the pre-determined date for full study unblinding the data analysis on the cellular or basic aspects of the study is lagging behind the clinical data outcome measures (though the data has been acquired) the Principal Investigator in consultation with the study sponsor may choose to un-blind the clinical outcome measures before the basic side data has been analyzed but compiled. Upon confirmation from the study sponsor, the principle investigator must make a written request to the designated party to unblind, hereto referred at the “*unblinder*”. The unblinder is the bio-statistician of the MFA, **[name]**. Upon receipt of an instruction to unblind, the unblinder will sign the request form, indicating their agreement to unblind. This form will then be taken to the pharmacy, **MFA’s IDS**, where a member of the IDS staff will take the form, and will give the unblinding study binder to the unblinder. The pharmacy will sign to indicate their release of the binder, and the unblinder will sign to indicate receipt of the binder. At this point in time the chain of custody of the pharmacy unblended binder has been transferred to the designated party to unblind. The form with all of the signatures will be provided to the study coordinator to be kept in the regulatory binder.

Possible Adverse Events, Definitions of Adverse Events and Management

Adverse event

An adverse event (AE) is defined as any untoward medical occurrence, including an exacerbation of a pre-existing condition, in a patient in a clinical investigation who received a pharmaceutical product. The event does not necessarily have to have a causal relationship with this treatment.

Serious adverse event

A serious adverse event (SAE) is defined as any AE which results in death, is immediately life-threatening, results in persistent or significant disability / incapacity, requires or prolongs patient hospitalisation, is a congenital anomaly / birth defect, or is to be deemed serious for any other reason if it is an important medical event when based upon appropriate medical judgement which may jeopardise the patient and may require medical or surgical intervention to prevent one of the other outcomes listed in the above definitions. Patients may be hospitalised for administrative or social reasons during the study (e.g. days on which infusion takes place, long distance from home to site,). These and other hospitalisations planned at the beginning of the study do not need to be reported as a SAE in case they have been reported at screening visit in the source data and have been performed as planned.

“Adverse Events of Special Interests” or “AEs of Special Interest” shall include:

1. Severe Allergic Reactions
2. Skin changes
3. Angio-edema
4. Heart attack or cerebral attack
5. Neurological manifestations
6. Acute Pancreatitis or acute hepatic failure
7. Acute worsening of renal function
8. Development of malignancy, occult or overt
9. Severe Documented Hypoglycemia (lab blood sugar less than 40mg%)

AEs of special interest are a list of medical topics that are under close surveillance. AE should be reported in an expedited manner similar to Serious Adverse Events even if they do not meet the seriousness criteria.

Please refer to the site master file for the complete list of AESIs (27-30).

Intensity of adverse event

The intensity of the AE should be judged based on the following:

- Mild: Awareness of sign(s) or symptom(s) which is/are easily tolerated
- Moderate: Enough discomfort to cause interference with usual activity
- Severe: Incapacitating or causing inability to work or to perform usual activities

Causal relationship of adverse event

Medical judgment should be used to determine the relationship, considering all relevant factors, including pattern of reaction, temporal relationship, de-challenge or re-challenge, confounding factors such as concomitant medication, concomitant diseases and relevant history. Assessment of causal relationship should be recorded in the case report forms.

Yes: There is a reasonable causal relationship between the investigational product administered and the AE.

No: There is no reasonable causal relationship between the investigational product administered and the AE.

Worsening of the underlying disease or other pre-existing conditions

Worsening of the underlying disease or of other pre-existing conditions will be recorded as an (S)AE in the (e)CRF.

Changes in vital signs, ECG, physical examination, and laboratory test results

Changes in vital signs, ECG, physical examination and laboratory test results will be recorded as an (S)AE in the (e)CRF , if they are judged clinically relevant by the investigator.

Responsibilities for SAE reporting: The Sponsor shall report (i.e., from signing the informed consent onwards through the trial defined follow-up period) all SAEs and non-serious AEs which are relevant for a reported SAE and Adverse Events of Special Interest (AESI) by fax or other secure method using BI IIS SAE form to the BI Unique Entry Point in accordance with timeline specified below.

- within five (5) calendar days upon receipt of initial and follow-up SAEs containing at least one fatal or immediately life-threatening event;
- Within ten (10) calendar days upon receipt of any other initial and follow-up SAEs.

Address for contact:

BIPI Unique Entry Point:

Boehringer Ingelheim Pharmaceuticals, Inc.

[name]

[contact]

E-mail: [contact].

For each adverse event, the investigator will determine the expectedness of the investigational drug to the AEs as defined in the Listed Adverse Events section of the Boehringer Ingelheim's (BI's Summary of Product Characteristics (SmPC) or Product Information (PI) for the authorised Study Drug provided by BI.

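### The early-unblinding exception in Section 4.4 does not state that the cellular data must be locked, or that those processing them stay masked, before allocation is released.

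*Combined protocol and SAP*

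**What the plan says.** Section 4.4 of the combined protocol and SAP deals with end-of-study unblinding under two sub-headings.

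Under *Time to unblind*, all subjects must have finished treatment and follow-up, and recruitment must be closed. In addition, "all data points and outcome measures for each research subject must have been collected, and ideally compiled". The lock covers both sides: "Prior to unblinding there will be a data lock on clinical outcome measures and basic side outcome measures and associated research data".

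Under *Procedure to unblind*, the ordinary route opens once the clinical and basic-science data "has been compiled and is data locked, the investigator can choose to unblind", with the sponsor's permission. An exception follows for the case where, "for unforeseen reasons, at the pre-determined date for full study unblinding", analysis of the cellular data is behind that of the clinical data ("though the data has been acquired"). The principal investigator, in consultation with the sponsor, then "may choose to un-blind the clinical outcome measures before the basic side data has been analyzed but compiled". Release is formal: "Upon confirmation from the study sponsor, the principle investigator must make a written request to the designated party to unblind". The biostatistician signs the request, and the pharmacy hands over the unblinding binder against signature.

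Section 2.1 places CD34+ cell number, function and gene expression under the primary objective, together with the urinary marker of kidney function.

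**The concern.** The exception lists what the cellular data must have reached before the clinical outcomes are unblinded, and a lock is not on the list. It also says nothing about who remains masked.

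The two data sets come from the same subjects, so the arm cannot be known for one and unknown for the other unless someone keeps them apart. The cellular readouts belong to the primary objective, and CD34+/KDR+ cells are one of the two measures behind the sample size in Section 5. If any of those readouts still needs judgement after the code is released, that judgement could be exercised with treatment known. The double masking would then be lost for a large part of what the trial sets out to show, and it could not be restored afterwards.

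**Working it through.** There is no design figure to reproduce. The check compares the three statements in Section 4.4, asks what a release reveals, and asks which cellular steps could still be open.

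**1. What each statement requires of the cellular data**

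| Requirement | Time to unblind | Ordinary procedure | Exception |
|---|---|---|---|
| Collected or acquired | Yes | Implied by compiled | Yes |
| Compiled | Ideally | Yes | Yes |
| Locked | Yes, both sides | Yes | Not stated |
| Analysed | Not required | Not required | Not required |

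**2. What the exception adds.** The ordinary route does not wait for completed analysis; compiled and locked data are enough. If the cellular data were already locked, a delay in analysing them would need no exception. The exception therefore changes something only if the cellular lock is relaxed. This is an inference from what the clause omits, because it does not expressly waive the lock.

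**3. What a release reveals.** Section 4.4 describes unblinding as telling the investigator, the clinical staff and the trial statistician what each enrolled subject received. One binder is handed over. No partial release is described, and nothing keeps the arm of a subject's cellular samples hidden once the arm of that subject's clinical data is known. Laboratory readers are not named among those told, but nothing says that they stay masked.

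**4. Which readouts could still be open.** The schedule in Section 4.5 puts the last cell harvest at week 12, and the assay description there has colonies counted on day 7 after plating. Section 3.1 puts the follow-up call 30 days after the last dose, with a visit window of 3 days either way. Assume that the last dose coincides with the week-12 visit and that the call counts as follow-up:

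- Last colony count to earliest unblinding: 30 - 7 = 23 days.
- If the visit falls 3 days after the last dose: 30 - 3 - 7 = 20 days.

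Colony counts should therefore be finished before the exception can be used. Even without the assumption about the call, the data must already have been acquired. That leaves processing after acquisition.

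**5. Rules for that processing.** Section 4.5 lists flow-cytometry percentages of double- or triple-positive cells, migration assays in triplicate, and 4 + 5 + 4 + 1 + 3 = 17 genes (lineage, antioxidant, apoptosis, endothelial function, chemotaxis). It gives no rules for gating, normalisation or rejection of assays, and no requirement for masked reading. That these steps exist and involve judgement is an assumption about laboratory practice; the documents do not describe them.

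**6. Extent.** Cells are harvested at weeks 0, 6 and 12 in 40 planned subjects, so at most 40 x 3 = 120 subject-visits are exposed. This is a ceiling on the data affected and not an estimate of bias.

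**The case against.** The best defence is that the two parts of Section 4.4 can be read together. The exception requires acquired and compiled data and lets only the analysis lag. Locking the compiled data and analysing them later would satisfy both parts. On that reading nothing is waived and the text is merely loose. This stands to the extent that a reader who infers a flat contradiction of the two-sided lock goes further than the words allow. It does not explain why the exception is needed at all, and it leaves the lock status unstated.

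The safeguards are also real. A reader might infer that the principal investigator can unblind alone, but the text requires unforeseen delay, a pre-determined date, sponsor consultation and confirmation, a written request, and documented release by the pharmacy. Those controls decide who authorises the release. They do not keep the people handling cellular data masked afterwards.

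Three further inferences are tempting and not supported:

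- That colonies would be counted with treatment known. The day-7 count and the requirement that data be acquired speak against it.
- That the cellular data are the whole primary outcome. The urinary markers share that place.
- That the bias can be expressed as a share of the planned 12-cell difference. The documents give no figure for a processing shift, and only a shift that differs between arms would bias the comparison.

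**Conclusion.** The point holds as a gap in the unblinding rule. The exception allows allocation to be released without stating that the cellular data are locked or that their processors stay masked, and it is not reconciled with the two-sided lock set out in the same section.

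The consequence is possible allocation-aware processing of cellular readouts under the primary objective. It rests on two assumptions: that gating, normalisation or exclusions remain open after acquisition and compilation, and that those doing this work learn the allocation. The documents neither confirm nor exclude either one. The size of any bias cannot be derived from them. The change is worth making because it costs little and has to come before the code is broken.

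**What to change.** Amend the exception under *Procedure to unblind* in Section 4.4 along these lines: no allocation code leaves the pharmacy until all cellular readouts, including flow-cytometry gating, gene-expression normalisation and exclusion of assays or outliers, have been finalised by masked staff and locked; only statistical analysis may follow unblinding.

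This keeps the flexibility that the exception seeks, since a late statistical analysis of locked cellular data need not hold up unblinding. It also brings the exception into line with the lock under *Time to unblind*. The cost is one sentence and a possible wait for the clinical results until the cellular data are locked.
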